The study will utilize clinical rating scales, functional assessments, patient-reported outcomes, postural and gait analysis, and wearable technology. The assessment outcomes will be evaluated to make recommendations based on their sensitivity and reliability in measuring real-world mobility and progression in patients with FA.

Background

Friedreich's ataxia is the most common recessive ataxic disorder in Caucasian populations, and most patients are homozygous for GAA expansion in the frataxin gene (FXN). The median age of disease onset is around 11 years; however, a wide age range (2-78 years) has been reported. Patients with FA frequently exhibit complex neurological phenotypes characterized by mixed sensory and cerebellar ataxia, muscle weakness due to pyramidal tract involvement, and other symptoms such as scoliosis and optic atrophy.

A recent online survey of 342 respondents with different types of ataxia identified gait and balance problems as the main symptoms that clinical trials should address, especially in an ambulatory group (1). Clinical rating scales such as Scale for the Assessment and Rating of Ataxia (SARA) or FAspecific scales such as Friedreich's Ataxia Rating Scale (FARS) are commonly used in clinical practice and research studies to determine the severity of ataxia. Several natural history studies employing these scales have provided invaluable insights into the temporal disease pattern and progression in FA over yearly intervals. In FA, the disease progression follows a rapid trajectory, depending on the age of onset (2) compared to dominant spinocerebellar ataxias (3).

However, inherent limitations of using clinical rating scales include the semi-quantitative and subjective nature, inter-rater variability and lack of sensitivity to detect change over short time periods (e.g. 6-12 months), with ceiling effects (4). Also, the small effect size of studies using clinical rating scales as the primary outcome means a large sample size is required (5), which is a significant barrier to the delivery of clinical trials in FA. Therefore, selecting robust clinical outcome measures which are reliable and sensitive to change is fundamental to testing novel therapeutic compounds, especially in drug studies with duration of less than one year.

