- Determine the feasibility of monitoring real-world mobility (habitual activity and gait) in FA patients and explore whether these outcomes are more sensitive than traditional clinical rating scales and controlled laboratory-based assessments.

Study Design and Setting

This study is designed as an observational pilot study involving 16 FA patients (ages 14-65 years). It is sponsored by Newcastle University but will take place at The Newcastle upon Tyne Hospitals NHS Foundation Trust (study site). The study will involve participants visiting at three time-points (Baseline, Month-6, and Month-12).

This protocol is part of a larger collaborative project also involving data collected via a separate study undertaken and managed by the Hertie Institute for Clinical Brain Research and Centre for Integrative Neuroscience (Tubingen).

Data (in an anonymised and pseudo-anonymised form) from both studies will be shared between collaborators and combined for data analyses.

Study Procedures

Participant Identification

Participants will be identified via neurology, paediatric and cardiology clinics at the Newcastle upon Tyne Hospitals NHS Foundation Trust. The direct clinical care team (of which the research team are part) will review clinic lists to identify potentially eligible patients.

Potentially eligible patients will be sent a study invitation letter along with a copy of the relevant Participant Information Sheet (PIS) or will be contacted by telephone/in person by their direct clinical care team (i.e. during a routine clinic) and invited to participate. Patients who are sent an invitation letter by post may also be contacted by telephone after the letter has been sent to check that it has been received.

The study will also be advertised via the websites and social media channels of charities and patient groups (e.g. Ataxia UK) and any volunteering participant will be able to contact the study team for enquiries regarding the study.

Where the age of the eligible participant is 14 or 15-years-old (i.e. under 16), parents/carers with parental responsibility will be provided with information about the study and the opportunity to ask questions about the participation of their child. The potential paediatric participant will also be provided with a suitable Participant Information Sheet (PIS).

Screening and Informed Consent

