In addition to the assessments conducted above, at the final study visit (Month-12) participants will be asked to provide feedback on their participation in the study. This will include their overall experience of the study and will also include discussion of any obstacles or challenges around use of wearable sensors. Information obtained from this feedback will be used to improve future studies.

Schedule of Events

	Assessments	Baseline	Month-6	Month-12
			(+/ -2 weeks)	(+/ -2 weeks)
	Eligibility Confirmation	X		
	Informed Consent	X		
	Re-confirmation of Consent (verbal)		X	X
Biometric Assessments	Demographics	X	X	X
	Anthropometrics	X	X	X
	Medical History & Concomitant Medications	X	X	X
c A	Review of Existing Medical Records	X	X	X
Siometri	Vital Signs	X	X	X
	Physical Examination	X	X	X
Clinical Eating Scales	FARS	X	X	X
	SARA	X	X	X
	INAS	X	X	X
	CCAS	X	X	X
Participant Reported Outcomes	PROMA	X	X	X
	NeuroQOL	X	X	X
	SF-36	X	X	X
	ABC Scale	X	X	X
	FSS	X	X	X
	FES-I	X	X	X
Eunctional Assessments	9НРТ	X	X	X
	BRAIN	X	X	X
	FGA	X	X	X
Evaluation of Gait and Postural Control	Static balance (stabiliometry) assessment [Force	X	X	X
	plates and wearable sensors (Opal and Ax6)]			
	10 MWT; Self-selected and Fast Pace [GAITRite	X	X	X
	and Wearable Sensors (Opal and Ax6)]			
	6 Minute Walk [GAITRite & Wearable Sensors (Opal & Ax6)]	X	X	X
	Wearable Sensors (Ax6) in Free-Living	X	X	X
	Environment (for 7 days post-visit)			
	Adverse Event Reporting	X	X	X
	Feedback from Participants			X

Note: Participant reported outcome measures are shaded in grey.

End of study

The end of study for each participant will be completion of their Month-12 visit assessments (including collection of real-world activity data via wearable sensor for seven days post visit).

The overall end of study will be defined as the last participant last visit (LPLV). However, analyses of study data will continue after this point.

Statistics

Outcomes generated from clinical rating scales and questionnaires will be collated into a single dataset for subsequent statistical analysis.

Data from this study will also be combined with data provided by Tubingen University collected as part of a separate study utilising a similar protocol.

Determining which outcomes (clinical rating scales, laboratory and real-world monitoring of mobility) are sensitive to disease progression will be achieved by assessing change over time across the 3 time points using ANOVA.

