We will determine the influence of sensor location (lower back vs. ankles) and configuration (single vs. multiple) on gait and balance outcomes by statistically comparing effect sizes of sensitivity to ataxia severity in cross-sectional and longitudinal analyses. We will also assess the test-retest reliability.

Gait outcomes derived from the wearable sensors will be validated against a gold standard (instrumented walkway) by quantifying the bias, intraclass coefficient and limits of agreement.

Correlations will be used to compare real-world mobility outcomes to traditional clinical rating scales and controlled laboratory-based mobility assessments.

Data analysis will be supported by the biostatistician at the WCMR.

Monitoring, Audit, and Inspection

The study may be subject to audit or monitoring by representatives of the Sponsor, Newcastle Hospitals, or inspection by regulatory authorities. Each investigator will permit study-related monitoring, audits and regulatory inspection including access to all essential documents and source data relating to the study. The site research team will follow local standard regulatory and quality assurance practices.

Adverse Event Reporting

Information on the participant's general health throughout the study will be collected and recorded in the participant's medical notes as part of the medical history data collection. However, due to the non-interventional nature of this study, only adverse events which directly relate to study procedures will be recorded as study adverse events.

Such adverse events will be documented in the participant medical records, recording causality and severity in addition to details of the event and will also be recorded on the study adverse event log held in the Investigator Site File (ISF). Copies of this log will be forwarded to Sponsor on a periodic basis for filing in the Trial Master File (TMF).

A Serious Adverse Event (SAE) for this study will be defined as an adverse event (as defined above) which meets any of the following criteria:

- Results in death
- Is life-threatening*
- Requires inpatient hospitalisation or prolongation of existing hospitalisation
- Results in persistent or significant disability/incapacity
- Consists of a congenital anomaly or birth defect
- Other important medical events that jeopardise the participant or require intervention to prevent one of the above consequences

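### The secondary objective asks whether real-world outcomes are more sensitive than rating scales and laboratory measures, but the only comparison stated between them is correlation, which cannot rank sensitivity

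*Protocol*

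**What the plan says.** Under Objectives and Outcome Measures, the last secondary objective covers the feasibility of monitoring real-world mobility and then adds a comparative question: to "explore whether these outcomes are more sensitive than traditional clinical rating scales and controlled laboratory-based assessments".

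The Statistics section has three sentences that bear on it:

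- **Change over time.** "Determining which outcomes (clinical rating scales, laboratory and real-world monitoring of mobility) are sensitive to disease progression" is to be achieved by "assessing change over time across the 3 time points using ANOVA". This names all three families of outcome, real-world monitoring among them.
- **Sensor location and configuration.** These are to be judged by "statistically comparing effect sizes of sensitivity to ataxia severity in cross-sectional and longitudinal analyses". This is a between-measure comparison of sensitivity, but it is stated only for sensors.
- **Real-world outcomes against the other two families.** "Correlations will be used to compare real-world mobility outcomes to traditional clinical rating scales and controlled laboratory-based mobility assessments".

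The Background says that rating scales suffer from "lack of sensitivity to detect change over short time periods (e.g. 6-12 months), with ceiling effects". Study Design and Setting describes an observational pilot of 16 participants seen at baseline, Month 6 and Month 12, with data to be combined with those of a separate Tübingen study.

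**The concern.** The objective is about relative sensitivity, and the analysis named for comparing the families measures association. A correlation does not alter when either variable is shifted or rescaled by a positive constant. It therefore carries no information on how large the mean change in one measure is, relative to its spread, compared with the other.

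The yardstick is also awkward. If the scales are as insensitive over 6 to 12 months as the Background argues, a better outcome need not correlate strongly with them. A weak correlation could then mean either a poor real-world measure or a good one.

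The ANOVAs answer a different question, namely whether each outcome changes at all. They include no contrast between outcomes. A result that is significant for one measure and not for another does not show that the two differ in sensitivity.

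At stake is the part of the study's recommendation that concerns real-world measures. The Study Summary says that recommendations will rest on sensitivity and reliability. As written, the comparative part of this objective has no analysis that estimates the quantity in question.

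**Working it through.** The protocol gives no effect size, power or precision figure for this objective, so there is no stated figure to reproduce. The check sets the objective beside the method and then illustrates the gap. Only n = 16 comes from the protocol. Every standardised response mean (SRM) and correlation below is an assumption.

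**Set-up.** Let A and B be 12-month changes in two measures in the same people, bivariate normal with unit SD and correlation rho. SRM = mean change / SD of change. Each measure's change is tested on its own with a two-sided one-sample t-test at 0.05. This simplifies the three-visit ANOVA to one contrast, baseline to Month 12. Each scenario has 20,000 simulated studies of n = 16.

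**1. Does correlation identify the more sensitive measure?**

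| True SRM A / B | rho | Mean sample correlation | Mean SRM difference (SD) |
|---|---|---|---|
| 0.5 / 0.5 | 0.3 | 0.29 | 0.00 (0.35) |
| 0.8 / 0.3 | 0.3 | 0.29 | +0.53 (0.37) |
| 0.3 / 0.8 | 0.3 | 0.29 | -0.53 (0.37) |
| 0.5 / 0.5 | 0.6 | 0.59 | 0.00 (0.27) |
| 0.8 / 0.3 | 0.6 | 0.59 | +0.53 (0.29) |
| 0.3 / 0.8 | 0.6 | 0.59 | -0.53 (0.29) |

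The correlation of changes is the same whether A is better, B is better or they are equal. The paired SRM difference separates the three cases.

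**2. Do separate tests of change identify it?** Take equal true SRMs of 0.5. The chance that exactly one measure is significant is P(A only) + P(B only):

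- rho = 0.3: 0.204 + 0.200 = 0.404
- rho = 0.6: 0.152 + 0.154 = 0.306

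So in about 31% to 40% of studies, two equally responsive measures would look different if judged by which one reached significance.

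**3. How precise would a direct comparison be?** Assume SRMs of 0.8 and 0.4 and rho = 0.3.

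- n = 16: simulated SE of the SRM difference 0.36 to 0.37; half-width 1.96 × 0.37 ≈ 0.73
- n = 32 (an assumed pooled size; the protocol does not give the Tübingen number): SE 0.25; half-width 1.96 × 0.25 = 0.49

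Both half-widths exceed the assumed true difference of 0.4. In the same scenario a percentile bootstrap 95% interval, without site strata, covers the true value in about 91% of studies at n = 16 and 93% at n = 32. It excludes zero in about 28% and in 41% to 44% of studies respectively.

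**4. Pooling.** For two equal-sized sites, pooled r = (r_w + dx·dy/4) / √((1 + dx²/4)(1 + dy²/4)), where r_w is the within-site correlation and dx, dy are the site shifts in SDs. With r_w = 0.50 and shifts of 1 SD:

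- opposite directions: (0.50 - 0.25) / 1.25 = 0.20
- same direction: (0.50 + 0.25) / 1.25 = 0.60

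The protocol gives no site difference, so the direction of any distortion is unknown. This supports estimating within site or adjusting for site, and nothing stronger.

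**The case against.** The best defence is that the plan handles sensitivity in its own sentence. The ANOVA sentence names real-world monitoring beside scales and laboratory measures, so change is examined in every family. The correlation sentence does not mention sensitivity, and it can be read as convergent validity, in line with the stated aim of validating instrumented measures against rating scales. This stands in part: the plan is not silent on whether real-world outcomes change. It does not supply the comparison, because no contrast between families is stated and correlation is the method named for comparing them.

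A second defence is that how ANOVA results are compared across families may be left to an analysis plan that is not shown. That would answer a complaint about missing detail. It does not answer the choice of an unsuitable comparison in the protocol itself.

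Three stronger readings are tempting, and the document supports none of them:

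- A reader might infer that the correlations are cross-sectional only. The text does not say so. The point does not depend on it, since correlations of change fail in the same way.
- A reader might infer that p-values will be compared across outcomes. Nothing says so. The 31% to 40% figure shows why such a comparison would not fill the gap; it does not describe the plan.
- A reader might infer that pooling with Tübingen will weaken the correlations. It could as easily strengthen them, and the protocol does not say that site will be ignored.

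Finally, the objective is secondary, worded as exploratory, and belongs to a 16-person pilot. This stands, and it limits the severity.

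**Conclusion.** The concern holds in this form: within-family change is analysed for all three families, but the only stated comparison of real-world outcomes with the others is correlation, and neither that nor separate ANOVAs estimates a difference in sensitivity. That correlation cannot rank responsiveness follows from its definition and needs no assumption. The 31% to 40% rests on n = 16, equal SRMs of 0.5, rho between 0.3 and 0.6, normal changes, and a single 12-month contrast in place of the three-visit ANOVA.

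It would go too far to say that the study cannot inform the objective. The data needed are scheduled at all three visits, and the team already plans the right kind of comparison for sensors. The primary objective, on laboratory measures, is not affected by this mismatch. Severity is moderate.

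**What to change.** Amend the Statistics section as follows.

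1. Extend the longitudinal effect-size comparison planned for sensors to this objective. Estimate the paired difference in 12-month SRM, real-world minus rating scale and real-world minus the laboratory equivalent, in participants who have both measures. Score every measure so that worsening has the same sign.
2. Name a short list of outcome pairs in advance, since the gait, activity and scale outcomes allow a great many.
3. Give a bootstrap confidence interval, resampling participants within site. Report it as an exploratory estimate and not as a confirmatory test.
4. Keep the correlations, add those of 12-month change, and label them supportive convergent validity. When data are pooled, estimate them within site or adjust for site; the real-world set-up differs, with one sensor in Newcastle and three in Tübingen.

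The cost is a change of wording and a little more analysis, with no extra visits or measurements. The drawback is imprecision: an SE of about 0.36 to 0.37 at n = 16 and 0.25 at an assumed n = 32, with percentile bootstrap coverage somewhat below nominal. The report should say so.

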Footfalls captured by the instrumented walkway will be processed and a battery of spatio-temporal gait outcomes will be extracted.

The following outcomes will be generated:

- Step length: distance in the direction of travel from the heel during foot contact to the contralateral heel during the next foot contact.
- Step time: duration from foot contact to contralateral foot contact
- Step velocity: step length divided by step time
- Stance time: duration from foot contact to when the foot is lifted off the ground
- Swing time: duration from when the foot is lifted off the ground to its next contact with the ground Step width: perpendicular distance between the heel (foot contact) and the direction of travel of the contralateral foot.

The mean, variability, and asymmetry of gait characteristics will be calculated. Custom algorithms developed at Newcastle University and Tubingen will be used to extract the same spatio-temporal gait outcomes outlined above (barring step width and step width variability) from the wearable sensors.

The gait assessments within the gait lab will be captured on video for the purposes of data veracity (to check for any anomalies in the data) during the processing/data analysis phase.

Habitual physical activity (real world activity) in the community will be measured by using a non-intrusive sensor (Axivity Ax6) on the lower back for seven consecutive days. A custom medical grade fixing is used to adhere the sensor to the skin (figure above). Previously tried and tested documents containing information and guidance will be provided to participants. The sensor will be set to pre-record for seven consecutive days to ensure a representative window of activity covering both weekday and weekend activity is obtained and given to the participant at the end of the laboratory session.

Following completion of recording, participants will return the sensor using a pre-paid, tracked envelope. Data will be downloaded from the sensor for processing. Outcomes of interest include daily time spent supine, sitting and moving as well as specific features of gait as outlined above (i.e. including walking speed, gait variability and asymmetry). We will compare this one sensor approach with the 3-sensor approach in the real-world assessment performed in Tubingen.

Collection of Feedback from Participants

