The REDCap system utilised in this study will be provided by The Newcastle upon Tyne Hospitals NHS Foundation Trust. It is independently maintained and supported by Newcastle Hospitals. It is hosted on secure cloud servers held by AIMES. AIMES are an NHS certified cloud system provider based in Liverpool, UK.

The Newcastle Joint Research Office (NJRO) Research Informatics Team, manage and retain responsible for maintaining the local system, ensuring appropriate and secure access to the specific trial eCRF at a Sponsor/site level.

Management of the study's REDCap eCRF will be as per the relevant (NJRO) SOPs. Further information relating to REDCap and its security at Newcastle Hospitals is available via the NJRO website: https://newcastlejro.com/about/informatics/redcap/

Data Handling and Record Keeping

The study will comply with the General Data Protection Regulations (GDPR), 2018.

Data entry will be performed by a member of the research team at the site. Access to the study REDCap database will be restricted to research team members and associated REDCap administrators within Newcastle Hospitals only. Access to other study databases (i.e. gait database) will also be restricted to authorised team members only. Permission to access the study databases will be issued by the Chief Investigator.

Within the study databases, participants will be identified by a unique study ID number. Participant DOB, email address and mobile phone number (see above) may also be captured on the REDCap database however no other personal identifiers will be used.

The link between the participant's unique study ID number and their name will be via the study enrolment log (also known as the Participant Identification Log) which will be held in the ISF.

Pseudo-anonymised data, obtained as part of a separate study undertaken by Tubngen University, will be provided to the study team and combined with data from this study for analysis. This will include upload of some data items to the study REDCap database. All relevant data transfer agreements will be put in place prior to the transfer of such data.

Gait data from the Newcastle study will also be transferred to Tubingen for analyses. This will be pseudo-anonymised and will also be subject to the relevant data transfer agreements. The gait data transferred will not include any of the video recordings.

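### Judging sensitivity to progression by a three-visit ANOVA makes the comparison between outcomes depend on how many patients supply each one, and that number may differ by outcome.

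*Protocol*

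**What the plan says.** The planned Newcastle sample is 16 (Study Summary Information; Study Design and Setting). The Statistics section adds the German data: "Data from this study will also be combined with data provided by Tubingen University collected as part of a separate study utilising a similar protocol". The next paragraph of that section covers rating scales, laboratory outcomes and real-world outcomes together. It says that finding which of them respond to progression will be done by "assessing change over time across the 3 time points using ANOVA".

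The same section plans two other comparisons. Effect sizes are to be compared for sensor location and configuration. Correlations are to relate real-world outcomes to rating scales and laboratory measures. The third secondary objective asks whether real-world outcomes are more sensitive than those two groups.

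Two other places bear on how many patients stand behind each outcome.

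- Evaluation of Postural Control, Gait and Habitual Physical Activity: Newcastle records home activity with a single lower-back sensor, and "We will compare this one sensor approach with the 3-sensor approach in the real-world assessment performed in Tubingen".
- Withdrawal Criteria, footnote: after a severe reaction to the adhesive, home sensor use may stop while the participant stays in the study for the remaining assessments.

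On the transfer of the Tübingen data, Data Handling and Record Keeping adds: "This will include upload of some data items to the study REDCap database". That sentence is about the database and does not say which outcomes are pooled.

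The protocol gives neither the Tübingen sample size nor a list of the outcomes that both centres record.

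**The concern.** The study exists to choose outcome measures, so the yardstick for choosing matters more than any single estimate. An ANOVA test answers whether there is evidence of change in the patients at hand. That evidence grows with the number of patients even when the true change is the same. If rating scales come from both centres and a real-world outcome from one, the scales have an advantage unrelated to their responsiveness.

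Real-world outcomes look most exposed. The recording set-up is known to differ between centres for them, and they can also be lost within Newcastle while the scales are kept. Correlation does not fill the gap: two outcomes can correlate strongly while one changes far more than the other relative to its noise. The third secondary objective could then be answered by who was measured rather than by which measure responds better.

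**Working it through.** **Inputs from the protocol.** Newcastle n = 16; three visits; ANOVA over time. The protocol gives no power calculation, so there is no stated figure to reproduce.

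**Assumptions.** Alpha 0.05. Tübingen n = 16 (range 8 to 24), so a pooled n of 32 (24 to 40). Linear mean change, equal correlation between visits, no extra between-centre variance. Let s be the 12-month mean change divided by the SD of that change.

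**Model.** With residual SD σ, the SD of change is √2σ and the mean change is D = s√2σ. Visit means are 0, D/2 and D, with squared deviations from their average summing to D²/2 = s²σ². The F test has df 2 and 2(n−1) and noncentrality λ = n·s².

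**Power at the same true change, s = 0.6**

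| n | λ = n × 0.36 | Power |
|---|---|---|
| 16 | 5.76 | 0.521 |
| 24 | 8.64 | 0.723 |
| 32 | 11.52 | 0.852 |
| 40 | 14.40 | 0.925 |

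The pattern does not hang on 0.6: at s = 0.5, power is 38% for n=16 and 70% for n=32, confirmed by simulation (0.382 and 0.697). At s = 0 it is 5% at every n, so the advantage needs a real change.

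**The same observed change.** When the observed means are linear, F = n·s²/2. For an observed s of 0.45:

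- n=16: F = 16 × 0.2025 / 2 = 1.62, p = 0.215
- n=32: F = 32 × 0.2025 / 2 = 3.24, p = 0.046

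The smallest observed change reaching p<0.05 is √(2·Fcrit/n):

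- n=16: √(2 × 3.316/16) = 0.644
- n=32: √(2 × 3.145/32) = 0.443

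**Wrong ordering.** Take a weaker outcome (true s = 0.45) and a stronger one (true s = 0.60, n=16). How often is the weaker significant and the stronger not, if they are independent? The stronger misses with probability 1 − 0.521 = 0.479.

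| n of weaker outcome | Its power | Weaker significant, stronger not |
|---|---|---|
| 16 | 0.315 | 0.315 × 0.479 = 0.151 |
| 24 | 0.465 | 0.465 × 0.479 = 0.223 |
| 32 | 0.597 | 0.597 × 0.479 = 0.286 |

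With equal n the reversal already happens in about 15% of cases. Unequal n (32 against 16) raises it to about 29%, so roughly half of the 29% is due to the imbalance.

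The same 16 Newcastle patients would supply both outcomes, so independence is a simplification. Simulating the same set-up with a within-patient error correlation of 0.5 gives about 23% with n=32 for the weaker outcome, and about 9% with n=16 for both. Correlation lowers both figures; the gap remains.

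**What does not depend on n.** The expected effect size is not inflated by a larger sample: at s = 0.5, mean partial eta-squared in simulation was 0.16 at n=16 and 0.14 at n=32. The distortion comes from judging by significance, not from the size of the estimates.

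**The case against.** A reader might infer from "This will include upload of some data items to the study REDCap database" (Data Handling and Record Keeping) that only some outcomes can be pooled. The protocol does not support that. The sentence concerns which Tübingen items go into REDCap. The sentence before it says the Tübingen data are combined with this study's for analysis, and excludes nothing. The Data Management section keeps gait-laboratory and sensor data outside REDCap even for Newcastle's own patients, so a partial upload says nothing about partial pooling.

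Three further points can be made against the concern.

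- One against three sensors does not prove that real-world outcomes cannot be pooled. The protocol does not say where Tübingen places its sensors; if one is on the lower back, a common single-sensor outcome may be derivable. This stands, so unequal n is a possibility and not an established fact.
- No rule says that outcomes are ranked or discarded by p-value, and effect sizes are already planned for sensor location and configuration. This stands in part. Those effect sizes do not extend to the progression comparison, for which ANOVA is the only method named, and significance is its natural reading.
- Analysis sets and n per outcome are commonly left to an SAP, which is not at hand. That is fair for the detail. But the protocol itself fixes the criterion, and the criterion is poorly suited to comparing outcomes that may come from different numbers of patients.

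**Conclusion.** The concern holds conditionally. The protocol names a yardstick whose result depends on n, applies it to data combined from two centres with protocols described only as similar, and gives reasons why n may differ by outcome. If outcomes are judged by ANOVA significance, one recorded in more patients can appear more sensitive at the same true change: power 52% against 85% for n=16 and n=32 at a standardised change of 0.6. A weaker outcome could be significant while a stronger one is not in about 29% of cases, against about 15% with equal n.

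These figures rest on an assumed Tübingen sample of 16, alpha 0.05, assumed changes of 0.45 and 0.60, independence between outcomes, and no added between-centre variance. It would go too far to say that shared outcomes will look more sensitive, or that any outcome is known to be Newcastle-only. If outcomes are compared by effect size, or on a common set of patients, this advantage in reaching significance disappears.

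**What to change.** Amend the Statistics section as follows.

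1. Compare sensitivity to progression between outcomes on standardised 12-month change with 95% confidence intervals, not on ANOVA significance.
2. For each such comparison, use only patients and visits with all the compared outcomes recorded in the same way. This means Newcastle alone where Tübingen did not record one of them in that way.
3. Obtain confidence intervals for differences between outcomes by resampling patients, keeping each patient's outcomes together.
4. Report pooled results for shared outcomes separately, with n per outcome, and list which outcomes are shared. The three-visit ANOVA can stay as a description of change within each outcome.

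This needs no new patients, visits or measurements, only wording and some extra analysis. The downside is precision: the head-to-head comparisons use fewer patients than the full pool, so their intervals will be wider. The pooled estimates are still reported.
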